## 5. STUDY DESIGN

The proposed design is a two-group, randomized, controlled trial. After providing consent and completing a baseline assessment, a total of 68 eligible BCS will be randomized to computerized cognitive training or computerized attention control. Training sessions have been standardized across the BrainHQ training and attention control groups with each group completing up to 40 hours over 10 week period (total of up to 40 hours), with the dose based on previous research. Outcomes will be assessed at baseline and immediately post-intervention (within 90 days).

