Neuropsychological testing, completion of questionnaires and collection of a blood sample for BDNF will be collected at two time points during the study. Baseline (T1) data will be collected prior to the initiation of the intervention or attention control computerized training. Follow up assessments and BDNF blood sample will be collected post-intervention within 90 days of completing the intervention or attention control computerized training (T2)

Serum for BDNF analysis and all biomarkers that are part of this study will be prepared by laboratory services at IU and will be securely and confidentially (blood sample code) stored in the Analyte Laboratory within the Translation Core of the Center for Diabetes and Metabolic Disease under management of [name] (Co-I). The BDNF serum levels will be batch analyzed following collection of all samples following the manufacturers' ELISA protocol. The ELISA assay has standards ranging from 7.8 to 500 pg/ml BDNF (this is the possible range for all samples).

The study will also examine biomarkers that can affect brain functioning including neurotropic factor, proinflammatory cytokines, cortisol, and dehydroepiandrosterone (neuro steroid) DHEA.

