ANCOVA, to compare the effects of cognitive training to attention control will be used. The dependent variables, cognitive performance measured post-intervention, will be the primary outcomes. The baseline cognitive performance will be adjusted for as a covariate. The other independent variables will be the fixed effect for training group (BrainHQ, attention control), the Time effect, and the interaction term of Time-by-Training Group. The primary test of interest will the Group effect, which compares the two randomized groups on the outcome. The second most important test will be the interaction test to determine whether change over time differs for the two groups. We will also assess the Time effect, which tests whether scores generally changed in one direction for both groups combined. In addition, to ensure equivalence across groups potential covariates will be adjusted for in the models on which the various intervention and control groups significantly differ after random assignment at a liberal p-value of <.10. Effect sizes between the two groups will be computed as differences between adjusted means divided by pooled standard deviations. The significance level will be <.05 for all tests of hypotheses. Aim 5 provides the estimation of the effect of cognitive training on serum BDNF. Similar to Aims 1 and 2, a GLMM will be fitted to the data to estimate this effect, while controlling for potential known confounding effects including, age, education, smoking status, body mass index, medications, physical activity (per DUKE Activity Status Index) that may influence BDNF interpretation prior to hypothesis testing; although the RCT design will likely balance these factors.

**Power analysis:** We are adequately powered for estimating effect sizes or preliminary efficacy (Aim 2). Sample size is based on Aim 2 preliminary tests of post-intervention efficacy of the intervention on continuous outcomes. A difference between means equal to 0.80 standard deviations represents a large effect size, a medium effect size is 0.50, and a small effect size is 0.20.96 Using the Nquery software, a sample size of 30 in each group will provide 86% power for a two-sided t test to detect a large effect size of 0.80 when alpha is .05, to detect small or medium effect sizes.

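### Section 10 mixes two models: in one the Time and Time-by-Group tests have no estimate, in the other the primary Group effect is about half the T2 difference

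*Combined protocol and SAP*

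**What the plan says.** **Assessments.** Section 5: "Outcomes will be assessed at baseline and immediately post-intervention (within 90 days"). Section 8.1 says that testing, questionnaires and the blood sample "will be collected at two time points during the study", T1 before the intervention and T2 after it. There is no later follow-up.

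**Response and covariate.** Section 10: "The dependent variables, cognitive performance measured post-intervention, will be the primary outcomes". The next sentence: "The baseline cognitive performance will be adjusted for as a covariate".

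**Other terms and their ranking.** The model also contains a fixed effect for training group, "the Time effect, and the interaction term of Time-by-Training Group". Three tests follow:
- Named as primary: "The primary test of interest will the Group effect, which compares the two randomized groups on the outcome".
- Ranked next after that one: "The second most important test will be the interaction test to determine whether change over time differs for the two groups".
- Added last, without a rank: "We will also assess the Time effect, which tests whether scores generally changed in one direction for both groups combined".

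The Project Abstract adds that significant interactions will be followed by simple main effects. Section 10 introduces the whole analysis as a linear mixed-effects, repeated-measures ANCOVA.

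**Missing data.** The missing-data paragraphs of Section 10 say that the mixed model makes use of participants with incomplete data. They plan a re-run with missing-data pattern as a categorical covariate, conditional on cell sizes. They also say that baseline is completed before randomisation, yet the list of two possible patterns appears to include one with only the post-intervention visit.

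**Sizing.** Two-sided t test, 30 per group, effect size 0.80, alpha .05, power 86%. Sixty-eight participants are to be randomised.

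**The concern.** The sentences on the dependent variable and the covariate describe ANCOVA of a single T2 score. The sentences on Time, the interaction and incomplete participants describe a model in which T1 is also a response. The two cannot both apply, and they place the treatment effect in different coefficients. In the first it is the Group coefficient, and Time terms have no content. In the second it is the Time-by-Group term, and a Group main effect is diluted by the baseline visit, where randomised arms do not differ on average.

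At stake is which number is reported as the primary result. An analyst who follows the first description finds that the second-ranked test has no estimate and that nothing replaces it. An analyst who follows the second can fit everything, but the named primary test and the planned effect size may then refer to an average over T1 and T2. With the text as it stands, that choice could be made after the data are seen.

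**Working it through.** **Inputs.** From Section 10: 30 per arm, effect 0.80 (SD 1), two-sided alpha .05, power 86%. From Section 5: 68 randomised and two visits. Assumed: 1:1 allocation; T1-T2 correlation r of 0.3, 0.5 or 0.7 (the documents give none); equal SDs at both visits; and, for the design matrices, 8 of 68 without T2 (68 - 60).

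**1. The stated power.** Noncentrality = 0.80 × √(30/2) = 3.098 with 58 df gives 86.1%. This reproduces the plan's 86%, so the sizing is a two-group comparison at T2.

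**2. Literal model, T2 as the only response.** There are 60 rows, all at T2. The columns are intercept, T1 score, Group, Time and Time × Group. Time is constant, so it equals the intercept up to scale, and Time × Group equals Group in the same way. Five columns less two duplicates gives rank 3.
- Time and Time-by-Group are not estimable; they add 0 df.
- The adjusted T2 group difference is estimable.
- A participant without T2 has no response row, so missing-data pattern takes one value in the fitted rows. Adding it gives rank 3 of 6, however many participants drop out, so the condition on cell sizes does not help.
- The Group coefficient needs care while the redundant columns remain. In one simulated data set a generalised-inverse fit split an ANCOVA Group coefficient of 0.968 into 0.484 for Group and 0.484 for Time-by-Group.

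Nothing is lost by dropping the interaction here. If T2 = a + b·T1 + g·Group, then T2 - T1 = a + (b - 1)·T1 + g·Group, with the same g. The adjusted T2 difference already tests differential improvement. Its power at 30 per arm (57 df, residual SD √(1 - r²)) is 89.1%, 94.0% and 98.9% for r = 0.3, 0.5 and 0.7.

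**3. T1 and T2 both as responses.** Intercept, Group, Time and Time × Group have rank 4 of 4. Adding the baseline covariate gives 5 of 5, and adding missing-data pattern as well gives 6 of 6. Pattern-by-time added to the model without the baseline covariate still fails (6 columns, rank 5).

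The Group main effect averaged over visits has expectation (0 + 0.80)/2 = 0.40. Without a baseline covariate, the person mean has variance (1 + r)/2, so the standardised effect is 0.40/√((1 + r)/2). The change-score (interaction) test has standardised effect 0.80/√(2(1 - r)). With 58 df:

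| r | Averaged effect, standardised | Power, averaged Group test | Power, interaction test |
|---|---|---|---|
| 0.3 | 0.496 | 47.2% | 73.1% |
| 0.5 | 0.462 | 42.1% | 86.1% |
| 0.7 | 0.434 | 37.9% | 97.6% |

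If baseline is also kept as a covariate and the person mean is analysed, the estimate is still halved. The test does not lose power, however, because (T1 + T2)/2 adjusted for T1 is half the ANCOVA contrast with half its residual. The halved estimate therefore applies to any averaged Group effect; the 38-47% applies only without the covariate.

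**4. An equivalent two-response model.** With equal baseline means, unstructured covariance and no baseline covariate, the T2 contrast agreed with completer ANCOVA to within 1.8e-8 over 36 simulated trials with dropout. When T1 is always observed, participants without T2 add nothing to the treatment contrast in either model.

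**The case against.** The strongest reply is that the sponsor meant a genuine two-visit repeated-measures model. The method is named as such, Time and the interaction are defined by change, and the missing-data text relies on incomplete participants contributing. On that reading nothing is inestimable. This stands, so a reader should not infer that the planned terms simply cannot be fitted. But that reading contradicts the two sentences fixing T2 as the dependent variable and T1 as a covariate, and it makes the named primary test problematic if Group is averaged over visits.

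A second reply is that software will drop the redundant terms and leave a correct ANCOVA. Often it will, and the comparison of the two arms on the post-intervention outcome is then the right one. It is not guaranteed, as the split coefficient above shows, and the plan should not depend on a software default.

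A third is that no hypothesis goes untested on the literal reading, so this is only wording. The first part is right. However, the wording decides which coefficient is primary, and the missing-pattern re-run is the only dropout sensitivity model in Section 10. The comparison of dropouts with completers, and the promise to describe possible bias, are unaffected.

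**Conclusion.** Section 10 combines two incompatible models and should be corrected. On the literal model, the interaction test, the Time test and the simple-main-effects follow-up have no estimate, and the missing-pattern re-run adds 0 df. On the two-response model these terms can be fitted, but an averaged Group effect would be about 0.40 for a true T2 difference of 0.80. Without baseline adjustment its power would be about 38-47% at 30 per arm, against the stated 86%. That range rests on the assumed correlations and equal SDs; the rank results do not.

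Two stronger inferences are tempting. One is that the efficacy analysis or the 86% is invalid. The documents do not support this: the adjusted T2 difference is estimable and the power figure reproduces. The other is that the primary Group test is sound as it stands. That holds only on the literal reading with the redundant terms removed. It also leaves open the effect of other terms Section 10 may add, namely covariates selected for imbalance at p<.10 and treatment dose, which are not endorsed here.

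**What to change.** Choose one model and name the T2 group contrast as the single efficacy test and the basis of the effect size. Either of these will do:
- ANCOVA of the T2 score on randomised group and T1 score; or
- a T1/T2 repeated-measures model with no baseline covariate, equal baseline means and unstructured covariance. Here the Time-by-Group term is the T2 contrast itself, not a second test.

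In Section 10, delete the separate Time and Time-by-Group tests; in the Project Abstract, delete the simple-main-effects sentence. If change within arms is of interest, report mean T2 minus T1 with a 95% confidence interval by arm, descriptively.

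Delete the missing-pattern re-run. State that participants without T2 do not inform the treatment contrast, and reconcile the list of missing-data patterns with randomisation after a completed baseline. If a dropout sensitivity analysis is wanted, impute T2 under a stated range of shifts for the missing scores.

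Say separately whether the p<.10 covariates and treatment dose enter this model. The cost is SAP and abstract wording only; no new data are needed.

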# 4. APPROACH

**PRELIMINARY STUDIES:** The proposed study will leverage the expertise of an interdisciplinary team of experts in cancer, neuro-psychological assessment, statistics and cognitive training in BCS). Our team has been internally (ACS) and externally funded (RWJF and Walther Cancer Institute) and have conducted multiple studies which have (1) documented clinically significant memory impairment in 52 BCS compared to age and education matched healthy control women; (2) examined the impact of perceived cognitive impairment in 134 BCS and found that those with more cognitive concerns had poorer QOL, including more depressive symptoms, lower well-being, poorer physical functioning, and greater fatigue; (3) interviewed 22 BCS which revealed that BCS incur cognitive concerns including memory and processing speed and that those deficits impact their self-esteem, social relationships, and work ability; and most recently (4) we completed the Advanced Cognitive Training in Breast Cancer Survivors (PI: [name]). With funding from the Robert Wood Johnson Foundation, we conducted a randomized controlled trial comparing two cognitive training interventions (memory and computerized cognitive training) to a wait-list control group in 82 female BCS at the IUSON.

Computerized cognitive training (InSight) compared to wait-list control, resulted in immediate and durable improvements in neuropsychological measures of (1) memory at post-intervention and 2-month follow-up (effect sizes=0.75 and 0.82; respectively; p<.01) and (2) processing speed at post-intervention and 2-month follow-up (effect sizes=0.55 and 0.67, p<0.05). InSight training also had the advantage of demonstrating improved perceived cognitive functioning, associated symptoms (less depressive symptoms, anxiety and fatigue), and quality of life. This important work represents one of the largest RCT in computerized cognitive training in BCS to date and the only one to include a neuropsychological battery. The next logical step is to build on this previous work and translate the findings to general practice.

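### Does the power statement claim that 30 per group can detect small or medium effects?

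*Combined protocol and SAP*

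**What the plan says.** The power paragraph of Section 10 (Data Analysis) bases the sample size on Aim 2 and on continuous outcomes measured after the intervention. It labels differences of 0.80, 0.50 and 0.20 SD as large, medium and small. It then states that "a sample size of 30 in each group will provide 86% power for a two-sided t test", and finishes the sentence with "to detect a large effect size of 0.80 when alpha is .05, to detect small or medium effect sizes".

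Section 5 (Study Design) says that "a total of 68 eligible BCS will be randomized to computerized cognitive training or computerized attention control". That is 34 per group if allocation is equal. The ratio is not given in words, and no dropout rate is stated.

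Section 4 (Approach) reports the team's earlier trial against a wait-list control. The effects are "memory at post-intervention and 2-month follow-up (effect sizes=0.75 and 0.82; respectively; p<.01") and "processing speed at post-intervention and 2-month follow-up (effect sizes=0.55 and 0.67, p<0.05"). It gives no effect size for perceived cognitive function.

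**The concern.** The sentence names one power figure and one effect size and then, after a comma, adds small and medium effects with no verb, figure or negation to connect them. A literal reader could take 86% to cover all three sizes. No other part of the document gives power at 0.50 or 0.20, or says that the trial is not powered for them. The paragraph opens by calling the study adequately powered for estimating effect sizes or preliminary efficacy, so nothing there corrects the impression.

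If the clause were a real claim, it would misstate what a non-significant result can show. Power at a medium effect is about one half on the stated calculation, and a small effect would nearly always be missed. The earlier trial's immediate post-training effect on processing speed was 0.55, which suggests that medium effects are not far-fetched for this intervention.

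**Working it through.** **Inputs.** From Section 10: 30 per group, two-sided two-sample t test, alpha .05, effects of 0.80, 0.50 and 0.20 SD. From Section 5: 68 randomised, taken here as 34 per group (equal allocation is an assumption).

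**Formula.** Power is P(|T| > t_crit), where T follows a noncentral t distribution with 2n − 2 degrees of freedom and noncentrality d × √(n/2). With n = 30, df = 58, t_crit = 2.002 and √(30/2) = 3.873. With n = 34, df = 66, t_crit = 1.997 and √(34/2) = 4.123.

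**The plan's own figure.** d = 0.80, n = 30: noncentrality 0.80 × 3.873 = 3.098, power 86.1%. The stated 86% reproduces. A one-sided test would give 92.2%, so the two-sided test named in the sentence is the one that was used.

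**The other two effect sizes, same test:**

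| Effect (SD) | Noncentrality, n = 30 | Power, n = 30 | Power, n = 34 |
|---|---|---|---|
| 0.80 | 3.098 | 86.1% | 90.2% |
| 0.50 | 1.936 | 47.8% | 52.9% |
| 0.20 | 0.775 | 11.9% | 12.8% |

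The smallest effect with 80% power is 0.74 SD at 30 per group and 0.69 SD at 34. So 86% holds at 0.80 or larger and not at 0.50 or 0.20, with or without dropout.

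**Effect of the planned baseline adjustment.** Section 10 adjusts for the baseline score, which the t test ignores. With a baseline-to-follow-up correlation r, the effect in residual SD units is about d/√(1 − r²). The documents give no r, so the range 0.3 to 0.7 is an assumption. At 30 per group:

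- d = 0.50: r = 0.3 gives 0.524 and 52%; r = 0.7 gives 0.700 and 76%.
- d = 0.20: 13% to 19%.
- d = 0.55: 55.4% unadjusted, 59% to 84% adjusted.

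The unadjusted figures are therefore a floor for the planned analysis, though on these correlations power at 0.50 and 0.20 stays below 86%.

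**What the sentence claims.** The preceding sentence keeps the three effect sizes apart. The figure is attached by name to one of them: "will provide 86% power for a two-sided t test to detect a large effect size of 0.80 when alpha is .05". The remainder has no figure of its own. The claim that can be checked is correct, and the rest is a fragment.

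**The case for a change.** The best case for a change is that a protocol should not print a sentence that can be read as a false power claim, and that stating 48% and 12% would cost one line. Section 14 expects negative findings to guide clinicians, so readers would benefit from knowing which effects a negative result cannot exclude. The 0.55 for processing speed makes this concrete: on the unadjusted test a true effect of that size would be missed about 45% of the time (100 − 55.4 = 44.6).

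Part of this stands. The clause is defective, the figures are right, and a reader would be helped by them. Three things limit it.

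- **The fragment may not be the authors'.** The text available here has visible reading damage elsewhere: a broken sentence in Section 2, and Table 1 mixed into the running text in Section 8.2. A lost negation would explain the clause fully, and the plan would then already state the limit. The power paragraph shows no other damage, so an authoring slip is equally possible. Only the source file can settle it.
- **The 0.55 comparison carries little weight.** The sample size rests on Aim 2, which Section 1.1 defines as perceived cognitive function; processing speed belongs to the objective measures of Aim 4. The abstract words its second aim as objective performance, so the comparison is not irrelevant. But the 0.55 came against a wait-list control, and with baseline adjustment the 45% becomes roughly 16% to 41% over the assumed correlations.
- **Power at effects the trial was not sized for is optional detail.** A sample-size statement is complete when it gives power at its design effect. The study describes itself as preliminary and leaves efficacy to a larger trial.

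**Conclusion.** No change to the plan follows. The closing clause is a clerical slip or a reading artefact, to be checked against the source file and restored or deleted. The 86% reproduces at 86.1% for 0.80 SD with 30 per group and holds for that effect or larger. The sentence gives no power for 0.50 or 0.20, so no stated figure is wrong. Tidying the clause alters neither the number randomised, nor the model, nor any test or estimate.

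If the team chooses to add the limit for readers, 48% and 12% are the figures for an unadjusted two-sided t test at 30 per group. They should be labelled as such, because the planned baseline adjustment raises them by an amount that depends on a correlation the documents do not give.

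The conclusion rests on the test, alpha and group size stated in Section 10. The 34-per-group figures also assume equal allocation and complete follow-up of all 68.
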